9.2. Adverse Event Preferred Term and Body/Organ System Summary Tables

Adverse events will be presented for the treatment-emergent, and post-treatment periods. Treatment-emergent period is the day of first dose of ALIS through 28 days after the last dose of study medication, end of treatment visit, or end of study visit, whichever is earlier.

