--	---

Protocol Amendment 3.1: 25 May 2017

*This protocol is solely for communicating information about the investigational drug between Insmmed Incorporated and study personnel. Information is not to be reproduced, abstracted or used for sharing of information for any other purpose, whatsoever, except with the written permission of Insmmed Incorporated.*

	physical examination (including vital signs, pulse oximetry and weight), SGRQ, and EQ-5D-3L will be performed. Unscheduled visits will occur as needed should subjects' symptoms worsen between visits.
Study Duration	This study will begin once a subject has met all inclusion and none of the exclusion criteria; the subject will receive treatment with LAI in the study for 12 months (excluding observational follow-up).  Subjects may remain in the study for up to a total of 13 months (12 months on treatment plus 1 month off-LAI treatment for safety follow-up). Subjects will enroll directly from the INS-212 study at their EOT visit.
Study Population	The study is designed to screen only those subjects who were randomized in the INS-212 study. It is expected that approximately 200 subjects will be eligible for and enroll in this study. All subjects enrolled will be given LAI 590 mg QD plus their multi-drug regimen for 12 months. This study is planned to be conducted at approximately 150 sites in North America, Europe, and Asia-Pacific.

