	
There is no sample size determination as this study follows the INS-212 study; eligible subjects who consent after Month 6 and complete the EOT visit of the INS-212 study will determine the sample size of this study.
 
Statistical Methodology
 
The INS-312 study will comprise of two analyses. The first analyses will assess the proportion of subjects achieving culture conversion (3 consecutive monthly negative sputum cultures) by Month 6; the time to culture conversion (defined by the date of the first of at least 3 consecutive monthly culture specimens that are MAC negative); and the mean change from Baseline in the 6MWT distance by Month 6 of the study, as well as the safety and tolerability of LAI. The latter analyses will be the final analyses at the completion of the study and will include all other endpoints.
 
The safety endpoints are the frequency of TEAEs, TEAEs leading to withdrawal from study, treatment-emergent SAEs, AEs of special interest, clinically significant abnormal laboratory test results, and vital signs measurements. The safety analysis will be performed for the safety population.
 
All AEs will be coded using the Medical Dictionary of Regulatory Activities (MedDRA). AEs starting between first study drug administration in INS-312 and 1 month after last study drug administration will be regarded as treatment emergent.
 
The number and percentage of subjects with TEAEs, TEAEs leading to withdrawal from study, and treatment-emergent SAEs will be tabulated by System Organ Class and Preferred Term overall and by the treatment arm in INS-212. Furthermore, the incidence of TEAEs by worst grade of severity will also be tabulated by System Organ Class and Preferred Term overall and by the treatment arm in INS-212.
 
AEs that are not treatment-emergent will be listed.
 
For all other safety data (vital sign measurements, clinical laboratory values, audiology test results, and physical examination findings) observed values and changes from Baseline for continuous variables, absolute and relative frequencies for categorical observations, and shift tables from Baseline to last observation will be summarized overall and by the treatment arm in INS-212 using descriptive statistics.
 
The proportion of subjects achieving negative sputum culture conversion by Month 12/EOT and Month 6 will be summarized overall and by previous treatment arm in INS-212. Kaplan Meier estimates for the distribution of time to culture conversion will be constructed for the treatment arms in INS-212. The changes in 6MWT distance, SGRQ, SGRQ-Part II, EQ-5D-3L, and subject-reported symptoms of NTM will be summarized across all the study visits overall and by the previous treatment arm in INS-212 for the safety population.

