### 5.3 ADMINISTRATION OF STUDY DRUG

LAI is administered daily by inhaling drug product that has been aerosolized in a PARI eFlow® nebulizer over approximately 14 minutes. Study drug will be administered daily by the subject except for the two days immediately prior to a scheduled study visit when sputum is collected (refer to Section 7.2.2). On the day of the study visit, after sputum is collected, the study drug

Protocol Amendment 3.1: 25 May 2017

*This protocol is solely for communicating information about the investigational drug between Insmad Incorporated and study personnel. Information is not to be reproduced, abstracted or used for sharing of information for any other purpose, whatsoever, except with the written permission of Insmad Incorporated.*

will be administered at the study site by study personnel. Written directions for preparing and administering the study drug will be provided to subjects.

Subjects who develop bronchospasm may be pre-treated with a bronchodilator before study drug administration. Subjects who were pre-treated with a bronchodilator in the INS-212 study should continue to be pre-treated in this study.

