## 9.6 SAFETY ANALYSIS

The safety endpoints are the frequency of TEAEs, TEAEs leading to withdrawal from study, treatment-emergent SAEs, AEs of special interest, clinically significant abnormal laboratory test results, and vital signs measurements. The safety analysis will be performed for the safety population.

All AEs will be coded using the Medical Dictionary of Regulatory Activities (MedDRA). AEs starting between first study drug administration and 1 month after last study drug administration will be regarded as treatment emergent (TEAE).

The number and percentage of subjects with TEAEs, TEAEs leading to withdrawal from study, and treatment-emergent SAEs will be tabulated by System Organ Class and Preferred Term overall and by the assigned treatment arm in INS-212. Furthermore, the incidence of TEAEs by worst grade of severity will also be tabulated by System Organ Class and Preferred Term overall and by assigned the treatment arm in INS-212.

AEs that are not treatment-emergent will be listed.

For all other safety data (vital sign measurements, clinical laboratory values, and physical examination findings) observed values and changes from Baseline for continuous variables, absolute and relative frequencies for categorical observations, and shift tables from Baseline to last observation will be summarized overall and by the assigned treatment arm in INS-212 using descriptive statistics.

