6.4.9. Visit Windows

Nominal visit windows will be used for all visits, except for EOT and EOS visits. Because EOT and EOS visits are conducted in place of the planned visit for subjects who prematurely end treatment or study participation, these visits also need to be mapped to the coincident visit.

For example, a subject discontinues treatment at the Month 4 visit. The site will conduct the EOT visit at Month 4 rather than the Month 4 visit, but for analysis purposes this visit should be used for the Month 4 summary as well as the EOT summary. Similarly, for the EOS visit. Thus, should it be appropriate, the EOT and EOS visit need to be mapped to the corresponding visit. Should the EOT or EOS visit map to a time that doesn't coincide with a scheduled visit, it will not be mapped.

Subjects who prematurely discontinue from the study, may not have an EOT visit. In this case the EOS visit will also be the EOT visit and should be mapped accordingly.

Table 4: Visit Windows (Days)

Visit Name	Visit Number	Target Anchor	Relative Target Day	Visit Window
Baseline	1	Last visit from Study INS-212	1	-2 to 1
Month 1	2		30	23 to 37
Month 2	3		60	53 to 67
Month 3	4		90	83 to 97
Month 4	5		120	113 to 127
Month 5	6		150	143 to 157

Visit Name	Visit Number	Target Anchor	Relative Target Day	Visit Window
Month 6	7		180	173 to 187
Month 7	8		210	203 to 217
Month 8	9		240	233 to 247
Month 9	10		270	263 to 277
Month 10	11		300	293 to 307
Month 11	12		330	323 to 337
Month 12 (EOT)	13		365	353 to 367
Month 13 (EOS)	14		420	413 to 427

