13.2	ADVERSE EVENTS.....	25
13.3	CLINICAL LABORATORY EVALUATION	27
13.4	VITAL SIGNS	28
13.5	PHYSICAL EXAMINATION	28
13.6	AUDIOLOGY TEST.....	28
14.	CHANGES TO PROTOCOL-SPECIFIED ANALYSES	28
15.	APPENDICES	29
15.1	APPENDIX A: PRESENTATION OF DATA AND PROGRAMMING SPECIFICATIONS.....	29
15.2	REFERENCES	32

List of Tables and Figures

Table 1: List of Abbreviations and Definitions	5
Table 2: Schedule of Events	12
Figure 1: Study Design	10

LIST OF ABBREVIATIONS

The following abbreviations are used in this document.

Table 1: List of Abbreviations and Definitions

Abbreviation	Term
6MWT	Six-minute walk test
6MWD	6-minute walk distance
AE	Adverse event
ATC	Anatomical/Therapeutic/Chemical
CI	Confidence interval
CSR	Clinical study report
CTCAE	Common terminology criteria for adverse events
DMC	Data monitoring committee
eCRF	Electronic case report form
EOS	End of study
EOT	End of treatment
EQ-5D-3L	Formerly EuroQol 5D, a generic health-status classification instrument
ICH	International conference on harmonisation
LAI	Liposomal amikacin for inhalation
MAC	Mycobacterium avium complex
MedDRA	Medical dictionary for regulatory activities
NTM	Nontuberculous mycobacteria
QD	Once daily
SAE	Serious adverse event
SAP	Statistical analysis plan
SGRQ	St. George's Respiratory Questionnaire
TEAE	Treatment-emergent adverse event
VAS	Visual analogue scale
WHO	World Health Organization

DEFINITIONS

Safety Population	The safety population is the set of all enrolled subjects who received at least 1 dose of Liposomal amikacin for inhalation (LAI).
-------------------	--

Adverse Event	Any untoward medical occurrence in a subject administered a pharmaceutical product and which does not necessarily have to have a causal relationship with this treatment.
Treatment-emergent Adverse Event	Treatment-emergent adverse events (TEAEs) are Adverse event (AEs) that occurred on or after the date of first dose of study medication in study INS-312 and within 1 month (28 days) after the last dose in study INS-312.

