13.2 Adverse Events

All AE summaries will be restricted to treatment-emergent AEs (TEAEs), which are defined as those AEs that occurred on or after the date of first dose of study medication in INS-312 and within 28 days after the last dose. If it can't be determined whether the AE is treatment emergent due to a partial onset date, then it will be classified as treatment emergent. All ongoing AEs from the INS-212 study will be documented as medical history for INS-312. At visits where study drug is administered, the occurrence of AEs will be assessed before and after administration of study drug. Any AE that has occurred before administration of the study drug on Day 1 in INS-312 and was resolved will be documented

for study INS-212. Verbatim terms on eCRFs will be mapped to preferred terms and system organ classes using the Medical Dictionary for Regulatory Activities (MedDRA).

Each AE summary will be displayed by INS-212 treatment arm and overall. Summaries that are displayed by system organ class and preferred terms will be ordered by descending order of total incidence of system organ class and preferred term within each system organ class. Summaries of the following types will be presented:

- Overall summary of TEAEs.
- Subject incidence of TEAEs and total number of TEAEs by MedDRA system organ class and preferred term.
- Subject incidence of most common ($\geq 5\%$) TEAEs and total number of TEAEs by MedDRA system organ class and preferred term.
- Subject incidence of serious TEAEs and total number of serious TEAEs by MedDRA system organ class and preferred term.
- Subject incidence of TEAEs and of serious TEAEs adjusted for exposure by MedDRA system organ class and preferred term. Subject-years incidence will be computed as the number of subjects who experienced the event during the study divided by the cumulative number of years all subjects were active in the treatment arm. For those subjects in the study at the time of data base cutoff (as example, for DMC review), their years in study will be censored at the time of database cutoff. To adjust for per 1,000 subject-years of exposure, the resulting incidence rate will be multiplied by 1,000.

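### Final SAP 9.2 can be read as ending the treatment-emergent period at the EOT visit, while the protocol runs it to 1 month after the last dose

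*SAP*

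**What the plan says.** Final SAP 9.2 opens the treatment-emergent period on the day of the first ALIS dose and closes it at "28 days after the last dose of study medication, end of treatment visit, or end of study visit, whichever is earlier". No other section of the final SAP that can be seen defines when the period ends. Section 9 only names the two periods, and 6.5.3 imputes partial dates.

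The other sources give one rule, tied to the last dose alone:

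- Protocol synopsis, Statistical Methodology: "AEs starting between first study drug administration in INS-312 and 1 month after last study drug administration will be regarded as treatment emergent". Protocol 9.6 repeats this.
- First-analysis SAP (accelerated submission), Definitions: "within 1 month (28 days) after the last dose in study INS-312".
- First-analysis SAP 13.2: "first dose of study medication in INS-312 and within 28 days after the last dose".

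The final SAP states in its Introduction that it is based on protocol Amendment 3.1, and no section declares a narrower window. The synopsis plans "12 months on treatment plus 1 month off-LAI treatment for safety follow-up", and AEs are assessed at the end-of-study (EOS) visit (protocol 6.4).

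**The concern.** The sentence in 9.2 allows two derivations.

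- **Reading A:** the window ends at the earliest of three dates: last dose + 28 days, the EOT visit, the EOS visit.
- **Reading B:** the window ends 28 days after the earliest of last dose, EOT visit and EOS visit.

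Reading B reproduces the protocol rule with 1 month taken as 28 days. Reading A contradicts it without saying so. TEAEs, treatment-emergent SAEs and AEs of special interest (AESIs) are components of the primary endpoint (final SAP 3.2.1), so a study programmer and an independent validator could build different flags for it.

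Under A, most AEs that start in the month set aside for off-drug safety follow-up stop being treatment-emergent. They go to the post-treatment tables (14.3.3.x), which by 9.2.1 and the table titles cover all, serious, fatal and hospitalised events. Those titles include no AESI or by-grade tabulation, and relatedness only for fatal SAEs (14.3.3.2.1.2). The rows of the overall summary 14.3.3.1.1 are in mock-ups outside these documents. Final counts would also rest on a different window from the first analysis.

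**Working it through.** The plan states no figure for this window, so the check is date arithmetic on its own schedule.

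**Inputs**

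- Gap from last dose to EOT: drug is taken daily "except for the two days immediately prior to a scheduled study visit when sputum is collected" (protocol 5.3), and protocol Table 3-1 marks no administration at Month 12/EOT. An on-time EOT on Day E therefore follows the last dose by 3 days: L = E − 3.
- EOT target days from final SAP Table 4: Day 365 (Month 12), and Day 180 or Day 30 if the EOT visit replaces Month 6 or Month 1.
- EOS: 1 month after EOT (protocol 6.4), taken as E + 30.
- 1 month = 28 days, from the first-analysis SAP.

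**Window end for a completer (E = 365, L = 362, EOS = 395)**

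- Reading A: min(362 + 28, 365, 395) = Day 365.
- Reading B: min(362, 365, 395) + 28 = Day 390.
- Protocol: Day 390, or Day 392 or 393 if a month is 30 or 31 days.

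A is short by 390 − 365 = 25 days and keeps 3 of the 28 post-dose days.

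**Share of the window removed under A** (protocol window ends at E + 25 with the 3-day gap, E + 28 with no gap)

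| EOT visit | 3-day gap | Last dose on EOT day |
|---|---|---|
| Month 12, Day 365 | 25/390 = 6.4% | 28/393 = 7.1% |
| Month 6, Day 180 | 25/205 = 12.2% | 28/208 = 13.5% |
| Month 1, Day 30 | 25/55 = 45.5% | 28/58 = 48.3% |

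A 14-day gap cuts 14 days. Once EOT is 28 or more days after the last dose, both readings end at last dose + 28 and the conflict disappears. Final SAP 6.4.9 also notes: "Subjects who prematurely discontinue from the study, may not have an EOT visit". In that case EOS stands in for EOT.

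**Effect on percent of subjects.** The documents give no event rates, so a constant onset rate is assumed. For a completer with incidence p over 390 days, incidence over 365 days is q = 1 − (1 − p)^(365/390):

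- p = 5% gives 4.69%.
- p = 20% gives 18.85%, a difference of 1.15 points, or 2.3 of the roughly 200 subjects expected (protocol 3.6.1).
- p = 90% gives 88.41%.

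Now suppose a fraction d stops, spread evenly over Months 1 to 11 with on-time EOT visits (an assumption). An event with 20% incidence in completers then changes as follows:

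- d = 0.2: 18.19% to 17.01%, a loss of 1.18 points.
- d = 0.4: 16.37% to 15.17%, a loss of 1.20 points.

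**Does the rest of the SAP settle the reading?** With EOS at Day 395, the post-treatment period lasts 395 − 365 = 30 days under A and 395 − 390 = 5 days under B, so the planned post-treatment tables fit A better. But Table 4 targets EOS at Day 420, which leaves 55 and 30 days. That target itself disagrees with an EOS 1 month after EOT, so it decides nothing. Under B the last dose, which by schedule precedes both visits, is the only date that can bind. The closing words then have no function.

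**The case against.** The strongest reply is that this is only a wording query. A single article introduces three parallel nouns, which fits reading B at least as well as A, and under B nothing changes. That supports calling the sentence ambiguous. It does not make B safe to assume, since B leaves the earliest-of clause idle. Under A the last-dose limb at least binds when EOT is late.

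Several points limit the size under A, and they stand:

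- The constant-rate figures may be too high. Protocol 5.3 reports that local respiratory events became less frequent with continued use, and a subject counts once per event. No chemistry, hematology, urinalysis or audiology is scheduled at EOS, so AESIs found by those tests would mostly surface by EOT.
- A subject who stops because of an AE need not have the 3-day gap, so the early-stop shares are illustrations.
- Tables 14.3.5.1 to 14.3.5.3 cover hospitalised SAEs with no treatment-emergent limit in their titles. Listings 16.2.23.7 and 16.2.23.8 show AESIs and serious AESIs for all subjects.
- TEAEs leading to withdrawal are barely touched, because such events normally start before EOT.
- Comparability with the first analysis is a lesser point, since that data cut already differs in follow-up.

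A sponsor could also want on-drug and off-drug events reported separately. That would be defensible if declared and justified as a change from protocol 9.6. It is not declared.

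**Conclusion.** The concern holds. Applied as a list of three end points, final SAP 9.2 breaks the protocol's TEAE definition. Only a second reading avoids this, and nothing in the text requires that reading. The ambiguity is certain. Which reading was intended cannot be told from the documents.

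Under A, an on-schedule subject loses 25 of 28 off-drug days. That is 6.4% of a completer's window and a larger share for early stoppers. The change in reported incidence is small: about 1.2 points for an event at 20%, given a constant onset rate and the assumed dropout pattern, and probably less where onset is early. Under B it is zero. Events are reclassified and remain in the outputs. Events that began before EOT still count, including later deaths from them. Laboratory and vital-sign components are unaffected. The point should be fixed because the flag drives primary-endpoint components, not because the numbers would move far.

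**What to change.** Replace the sentence in final SAP 9.2 with a single rule: treatment-emergent means onset from the first INS-312 dose through 28 days after the last INS-312 dose, regardless of the EOT or EOS visit date, and post-treatment means onset after that. State that 28 days stands for the protocol's 1 month, as in the first-analysis SAP. Build the TEAE (14.3.1), SAE (14.3.2), post-treatment (14.3.3), AESI (14.3.6 and 14.3.7) and cough (14.3.8) tables on that flag. If a cut at EOT was intended, declare and justify it as a departure from protocol 9.6.

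The cost is one sentence and one derived variable. If the programs followed reading A, TEAE percentages may become slightly less favourable. The post-treatment tables will hold few events.

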9.2.1. Tabulations of Adverse Events

Adverse events will be tabulated presenting the incidence and percentage of subjects along with the number of events by and across prior INS-212 treatment arms. Incidence of an adverse event is the number of subjects reporting the adverse event at least once. The denominator for the percentage is the number of subjects receiving the treatment within the analysis population for the by treatment arm tabulation and total number of subjects enrolled and receiving treatment for the total.

Incidence, percentage, and number of AEs will be reported for subjects reporting at least one AE, within the system/organ class (SOC), and by preferred term within the SOC. Adverse tabulations will be generated for the following:

- Pre-treatment AEs
 - All
 - Serious
 - All
 - Fatal

- Leading to hospitalization
- Treatment-Emergent
 - AEs
 - All
 - Common ($\geq 5\%$)
 - Related to study treatment
 - Leading to withdrawal from study
 - Leading to withdrawal of study treatment
 - Leading to withdrawal of ALIS
 - Leading to withdrawal of MDR
 - Leading to withdrawal of both ALIS and MDR
 - Resulting in study drug interruption
 - Resulting in interruption of ALIS
 - Resulting in interruption of MDR
 - Resulting in interruption of both ALIS and MDR
 - By maximum toxicity grade
 - By relationship to ALIS
 - Related to nebulizer
 - Serious AEs
 - All
 - Common ($\geq 5\%$)
 - Related to study treatment
 - Leading to withdrawal from study
 - Leading to withdrawal of study treatment
 - Leading to withdrawal of ALIS
 - Leading to withdrawal of MDR
 - Leading to withdrawal of both ALIS and MDR
 - Resulting in study drug interruption
 - Resulting in interruption of ALIS
 - Resulting in interruption of MDR
 - Resulting in interruption of both ALIS and MDR
 - By maximum toxicity grade

- By relationship to ALIS
- Resulting in hospitalization
- Related to nebulizer
- Fatal
- AEs of Special Interest
 - All
 - Common ($\geq 5\%$)
 - Related to study treatment
 - Leading to withdrawal from study
 - Leading to withdrawal of study treatment
 - Leading to withdrawal of LAI
 - Leading to withdrawal of MDR
 - Leading to withdrawal of both LAI and MDR
 - Resulting in study drug interruption
 - Resulting in interruption of LAI
 - Resulting in interruption of MDR
 - Resulting in interruption of both LAI and MDR
 - By maximum toxicity grade
 - By relationship to LAI
 - Related to nebulizer
- Serious AEs of Special Interest
 - All
 - Common ($\geq 5\%$)
 - Related to study treatment
 - Leading to withdrawal from study
 - Leading to withdrawal of study treatment
 - Leading to withdrawal of LAI
 - Leading to withdrawal of MDR
 - Leading to withdrawal of both LAI and MDR
 - Resulting in study drug interruption
 - Resulting in interruption of LAI
 - Resulting in interruption of MDR

- Resulting in interruption of both LAI and MDR
 - By maximum toxicity grade
 - By relationship to LAI
 - Related to nebulizer
- Post-Treatment AEs
 - All
 - Serious
 - All
 - Fatal
 - Leading to hospitalization

For related AEs tabulations and for adverse event tabulations by relationship to ALIS, an AE will be considered related if it is ‘definitely’, ‘probably’, or ‘possibly’ as indicated on the CRF. The related AEs tabulations will present only those AEs deemed related. The adverse event tabulations by relationship to ALIS will present a column for related and another for not related AEs.

Tabulations by maximum toxicity grade will report subjects only once at the highest toxicity grade reported with the summary level (eg, SOC, preferred term).

